10.7 INJECTION-SITE EXAMINATION

Injection-site reactions can occur with injection of CAM2038 or placebo. The injection site will be visually inspected for evidence of itching, erythema/redness (with erythema/redness rating), swelling (with swelling rating) and any other abnormalities.

Results from the injection-site examinations will be summarized and listed.

AEs that are believed to be associated with injection procedures will be summarized similarly to how other AEs are summarized (i.e., AEs not associated with injections).

10.8 URINE DRUG SCREEN

Urine drug screen will be summarized and listed.

10.9 COWS

The Clinical Opiate Withdrawal Scale (COWS) data will be summarized and listed.

10.10 SOWS

The Subjective Opiate Withdrawal Scale (SOWS) data will be summarized and listed.

10.11 C-SSRS

Columbia–Suicide Severity Rating Scale (C-SSRS) data will be summarized and listed.

11. IDENTIFICATION AND SUMMARY OF PROTOCOL DEVIATIONS

Major protocol deviations from entry criteria and treatment compliance will be summarized as far as they can be extracted from numeric or coded study data.

12. DATA QUALITY ASSURANCE

Accurate and reliable data collection will be ensured by verification and cross check of the CRFs against the Investigator's records by the Study Monitor (source document verification) and by the maintenance of a drug-dispensing log by the Investigator. Collected data will be entered into a computer database and will be subject to electronic and manual quality assurance procedures.

Additionally, due to the observations identified in the two sites that have been excluded from the primary ITT dataset (Sites 068 and 077), additional measures were taken to assure the quality of study conduct and data collection from other top sites; these were sites that enrolled more than 10 subjects in the study. The Sponsor's Quality Department, in parallel with an independent third-party auditor, conducted quality visits to these sites, and the results of revealed no critical or major findings or observations that would impact the quality of the data.

14. APPENDICES

14.1 APPENDIX A — IMPUTATION ALGORITHM FOR PARTIAL AND MISSING DATES

This section describes missing date imputation methods.

For Adverse Events

If the onset date is completely missing, the onset date is set to the date of randomization.

If the year is present, and month and day are missing, or if the year and day are present, and the month is missing:

- If year = year of randomization, then set month and day to month and day of randomization
- If year < year of randomization, then set month and day to December 31
- If year > year of randomization, then set month and day to January 1

If month and year are present and day is missing:

- If year = year of randomization and
 - If month = month of randomization, then set day to day of first dose
 - If month < month of first dose, then set day to last day of month
 - If month > month of first dose, then set day to first day of month
- If year < year of randomization, then set day to last day of month
- If year > year of randomization, then set day to first day of month

For all other cases, set the onset date to the date of randomization.

Concomitant Medications/Medical History

For start date

- If start date is completely missing, start date will not be imputed
- If year is present and month and day are missing, or if year and day are present and month is missing, set month and day to January 1
- If year and month are present and day is missing, set day to first day of month

For end date

- If end date is completely missing, end date will not be imputed
- If year is present and month and day are missing, or if year and day are present and month is missing, set month and day to December 31
- If year and month are present and day is missing, set day to last day of the month

Note that if both start and end dates are missing, the medication will be classified as concomitant.

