5.4 SAFETY POPULATION

The Safety Population will include all subjects who have received any dose of study medication. Analyses based on this population will group subjects according to the treatment they received rather than the treatment they were randomized to receive. All safety analyses will use the Safety Population.

In the primary safety summaries, data for Sites 068 and 077 mentioned in [Section 5.2](#) will be excluded, due to an inability to verify compliance with adverse event reporting requirements, leading to possible under-reporting of adverse events. However, supportive safety summaries will include the data from Sites 068 and 077.

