10.2 ADVERSE EVENTS

All AE and serious adverse event (SAE) terms recorded on the CRFs will be coded by primary system organ class (SOC) and will be mapped to a preferred term using the MedDRA. The Investigator will assess AE severity and relationship to the study treatment.

A treatment-emergent adverse event (TEAE) is defined as any AE with an onset date on or after the first dose of CAM2038, or any ongoing event on the date of first dose that worsens in severity after the first dose of CAM2038. Only TEAEs with an onset date prior to date of last dose plus 30 days will be tabulated in summary tables. For the purpose of calculating TEAEs and inclusion in summary tables, incomplete onset dates will be imputed as detailed in Appendix A.

AEs will be summarized by the number and percent of subjects in each primary SOC and preferred term, and subjects will be counted only once for each primary SOC and each preferred term. Summary tables of AEs by primary SOC, preferred term, and intensity will be provided. If a subject has more than one AE coded to the same preferred term, the subject will be counted only once for that preferred term by using the event with the highest intensity. Similarly, if a subject has more than one AE within a primary SOC category, the subject will be counted only once in that SOC category by using the event with the highest intensity.

AEs by primary SOC, preferred term, and relationship to study drug will be provided as well. If a subject has more than one AE coded to the same preferred term, the subject will be counted only once for that preferred term by using the most related event. Similarly, if a subject has more than one AE within a primary SOC category, the subject will be counted only once in that primary SOC category by using the most related event.

In addition, SAEs by primary SOC and preferred term will be provided. Deaths and SAEs will be summarized similarly to AEs. All adverse event tables will also include the total number of events, counting multiple events per subject.

AEs, Injection-related AEs, and other (non-injection related) AEs will be presented by treatment group and overall. Summaries of these AE subsets will be presented for the following categories:

- Study drug related AEs
- AEs by intensity
- AE relationship to injection
- Possibly study drug related AEs, by intensity
- AEs reasonably related to injection, by intensity
- SAEs
- AEs that led to discontinuation
- SAEs that led to discontinuation

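### The SAP's rule for incomplete AE onset dates mixes randomisation with an undefined first dose, can re-date titration events to randomisation or later, and fails for subjects never randomised

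*SAP*

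**What the plan says.** SAP section 10.2 defines a TEAE by onset, as "any AE with an onset date on or after the first dose of CAM2038", or by worsening of an event already present at that dose. For TEAE status and the summary tables, "incomplete onset dates will be imputed as detailed in Appendix A".

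For AEs, Appendix A (SAP section 14.1) then works as follows:

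- No date at all: "If the onset date is completely missing, the onset date is set to the date of randomization".
- Month missing: "If year = year of randomization, then set month and day to month and day of randomization". An earlier year gives 31 December and a later year 1 January.
- Only the day missing, in the year of randomisation: "If month = month of randomization, then set day to day of first dose". Other months are compared with the month of first dose. An earlier month gives its last day; for a later one, "If month > month of first dose, then set day to first day of month".
- Remainder: "For all other cases, set the onset date to the date of randomization".

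The appendix does not say whether first dose means the first CAM2038 dose or the first randomised dose.

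SAP section 5.4 does not require randomisation for the safety set: "The Safety Population will include all subjects who have received any dose of study medication". SAP section 3 places the titration phase within the scope of the plan.

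**The concern.** CAM2038 starts at the beginning of titration. Protocol section 7.4 requires at least 2 weeks on a stable dose before randomisation, and section 6.1 allows up to 10 weeks of titration. The two anchor dates can therefore fall in different months. A rule that tests a month against one date and fills in the day from the other can return a date that neither supports.

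At stake are the recorded onset, the phase to which an event belongs, and in some cases whether it counts as treatment-emergent. Every randomised placebo subject has already received CAM2038, and SAP section 10 presents safety data by drug received. For a placebo subject, onset relative to randomisation is what separates an event on open-label CAM2038 from one on placebo. Subjects who fail titration have been dosed, but have no randomisation date to put into the rule.

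**Working it through.** The plan states no figure on this point, so there is none to reproduce. The check has three parts.

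**1. Single cases.** First dose is read as the first CAM2038 dose, the term used in SAP section 10.2. All dates fall in one calendar year.

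| First CAM2038 dose | Randomised | True onset | Recorded as | Imputed | Result |
|---|---|---|---|---|---|
| 6 March | 15 May | 20 March | March | 15 May | Equal to the first-dose month, so no month branch fits and the remainder rule applies. The known month is lost; titration becomes double-blind |
| 6 March | 15 May | 20 April | April | 1 April | Stays in titration |
| 6 March | 15 May | 20 May | May | 6 May | Double-blind becomes titration |
| 27 March | 15 May | 3 May | May | 27 May | Titration becomes double-blind |
| 31 March | 1 June (62 days later) | any day in June | June | 31 June | No such date |

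Months are also compared without their years. With first dose in December and randomisation the next February, an AE recorded as March is treated as earlier than first dose, because 3 < 12.

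**2. Share of incompletely dated events that move.** The rules were coded branch by branch and run on 100,000 simulated subjects per scenario. These assumptions are not in the documents: randomisation uniform over a year; onset uniform within each phase; titration uniform over 14 to 70 days, with fixed 28 and 70 days as the range; pre-dose onset 1 to 28 days before first dose. The double-blind phase is 84 days. The code was lenient: it compared year and month together and cut impossible dates back to the end of the month.

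| Missing part | Movement | First dose = first CAM2038 dose | First dose = first randomised dose |
|---|---|---|---|
| Day | Titration to randomisation or later | 46% (70-day titration 20%; 28-day 88%) | 40% (21%; 53%) |
| Day | Double-blind to before randomisation | 6% (9%; 0.2%) | 0% |
| Month and day | Titration to randomisation or later | 94% (90%; 96%) | 94% (90%; 96%) |
| Whole date | Titration to randomisation or later | 100% | 100% |

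Pre-dose events became TEAEs in about 52% of cases with the day missing, 96% with month and day missing, and 100% with no date, under either reading.

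**3. Subjects without a randomisation date.** Protocol section 11.4 gives 340 randomised and a titration success rate of 60%. If that rate applies to subjects dosed:

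- dosed = 340 / 0.60 = 567
- never randomised = 567 − 340 = 227, and 227 / 567 = 40%

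The same section puts enrolment at 875. That cannot be the number dosed at this rate, since 0.60 × 875 = 525, not 340. The 227 therefore depends on the stated assumption. Whatever the number, every AE branch needs a randomisation date, including the remainder rule.

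**The case against.** The best defence is that SAP section 9.2 treats the randomisation date and the first randomised treatment date as the same. If first dose in Appendix A means the first randomised dose, the anchors coincide. The quoted line then returns the randomisation date, no known month is overwritten in the day-missing branch, and the reverse movement disappears. That is a fair reading, but it only removes the mixing. About 40% of day-missing titration events still move, because randomisation is then the anchor for a definition that starts at the first CAM2038 dose. Never-randomised subjects still have no rule.

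A reader might go further and infer that many titration events are moved and that the double-blind safety comparison is distorted. The documents do not support this:

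- They give no count of AEs with incomplete dates. AEs are asked about at each clinic visit, and titration visits are weekly, so such dates may be few.
- A titration event re-dated to randomisation remains a TEAE. SAP section 10.2 presents AEs by treatment group and overall, with no split by phase. Without such a split, moving the date changes no count.
- Titration events precede a 1:1 randomisation, so misdated ones should fall about equally on both arms. That would raise both rates and pull ratios towards 1, but would not by itself bias the risk difference.
- SAP section 10 has no pre-specified safety outcome and calls any formal comparison post hoc.

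It is also unclear whether never-randomised subjects enter the arm-level tables. SAP section 7.1 counts the primary Safety Population as a share of randomised subjects, whereas section 5.4 defines it by any dose. They have no arm, so they cannot affect the contrast between arms.

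**Conclusion.** The rule is wrong as written and should be corrected. This is a stated algorithm that returns wrong or impossible dates under the literal reading, and no date for dosed subjects who were never randomised under either reading. The harm is to onset dating, phase attribution and some TEAE classifications; a bias between arms is not shown.

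The shares apply only to AEs with incomplete dates and rest on the uniform-date assumptions and the assumed titration lengths. How many events are affected cannot be computed from the documents. Most of the movement comes from the branches that default to randomisation, rather than from the quoted line alone, which can move an event either way.

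**What to change.** **TEAE status.** Define first dose as the first CAM2038 dose and use its full date, with year and month compared together, as the only anchor:

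- same month and year as first dose: the first-dose date;
- any other known month: the first day of that month;
- year only, in the first-dose year, or no date at all: the first-dose date;
- year only, later year: 1 January; earlier year: 31 December.

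This also covers subjects never randomised. In the simulation, a first-dose anchor reduced movement of titration events into the double-blind phase to 0%. It did not reduce the share of pre-dose events counted as TEAEs, which stayed at about 52%, 96% and 100%. That is a conservative convention, and the SAP should say that it is intended.

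**Phase.** The single anchor creates the reverse error. It dated before randomisation about 17% to 18% of double-blind events with the day missing, 88% with year only, and all with no date. So if any table separates phases or attributes events to randomised treatment, add a separate step against the first double-blind dose. Use the known month and year and the AE end date, assign to titration if the end date precedes randomisation, and state one fixed rule for events that remain ambiguous, including those with a later or missing end date.

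The cost is appendix wording and minor programming, best done before unblinding. No new data are needed.
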